8.3.3. Discontinuation of Study/Site Termination by Sponsor or Health Authority

The Sponsor or Health Authority may terminate the study for reasonable cause. Conditions that may warrant termination of the study include, but are not limited to:

- Discovery of an unexpected, serious, or unacceptable risk to patients enrolled in the study
- Sponsor decision to suspend or discontinue testing, evaluation, or development of the study drug
- Failure of the Investigator to comply with the approved protocol, pertinent guidelines, and/or regulations
- Submission of knowingly false information from the Investigator to the Sponsor and/or regulatory authorities

Should the study be terminated early, the Sponsor will notify the national competent authority and the IRB/IEC according to local requirements.

8.3.4. Replacements

If it is determined at any point that a patient's Screening data does not satisfy Inclusion Criterion number [2c](#), Exclusion Criterion number [1](#), and/or Exclusion Criterion number [2](#), after receiving at least 1 dose of investigational product (eg, patient local laboratory data used to confirm eligibility criteria are subsequently determined by a central laboratory to no longer satisfy eligibility criteria), the patient will be discontinued from the study and may be replaced. Early termination procedures will be performed on patients who are terminated early ([Section 8.3.1](#)) and all AEs will be collected until 56 days after the patient's last dose of study drug ([Section 11.7.6.1](#)).

As described in [Section 15.3](#), the Full Analysis Set (FAS) will be based on a modified intent to treat (mITT) approach, and the patients discontinued from the study for the reasons described above will be excluded from the FAS. The aim of the replacement process is to yield a FAS that includes the planned number of patients all satisfying key inclusion and exclusion criteria.

8.3.5. End of Study Definition

The end of the study is defined as the date of the last patient's last visit in the Extension Period.

9. STUDY TREATMENT

9.1. Materials and Supplies

9.1.1. Description of Study Drugs

ALXN1210, a recombinant, humanized anti-C5 monoclonal antibody composed of two 448 amino acid heavy chains and two 214 amino acid light chains, is an IgG2/4 kappa immunoglobulin consisting of human constant regions, and murine complementarity-determining regions grafted onto human framework light- and heavy-chain variable regions. ALXN1210 is produced in Chinese hamster cells and was designed through minimal targeted engineering of eculizumab by introducing 4 unique amino acid substitutions to its heavy chain to extend antibody half-life. ALXN1210 and eculizumab share over 99% primary amino acid sequence identity and have very similar pharmacology.

ALXN1210 drug product is supplied for clinical studies as a sterile, preservative-free 10-mg/mL solution in single-use vials and designed for infusion by diluting into commercially available saline (0.9% sodium chloride injection; country-specific pharmacopeia) for administration via IV infusion.

Refer to [Table 4](#) and the current IB for additional information.

Table 4: Study Drug

Product Name	ALXN1210
Dosage Form	Concentrated solution (10 mg/mL) for infusion
Route of Administration	Intravenous infusion
Physical Description	Clear to translucent, slight whitish color, practically free from particles
Manufacturer	Alexion Pharmaceuticals, Inc. or Contracted Manufacturing Organization

9.1.2. Study Drug Packaging and Labeling

ALXN1210 is packaged in United States Pharmacopeia (USP)/ European Union Pharmacopeia (EP) Type 1 borosilicate glass vials and stoppered with a butyl rubber stopper with an aluminum overseal and a flip-off cap. Study drug will be supplied in kits. Please refer to the ALXN1210 Pharmacy Manual for details.

ALXN1210 orders will be released to each site upon receipt of all required documents based upon applicable regulations and once the site is activated in IXRS[®].

9.1.3. Study Drug Storage

Upon arrival of the study drug kits at the study site, the pharmacist (or trained designee) should promptly remove the study drug kits from the shipping cooler and store them in their original cartons under refrigerated conditions at 2°C to 8°C (35°F to 47°F) and protected from light. ALXN1210 should not be frozen. Study drug must be stored in a secure, limited-access storage area, and the temperature must be monitored daily.

The admixed drug product should be at room temperature prior to administration. The material must **not** be heated (eg, by using a microwave or other heat source) other than by ambient air temperature.

Please consult the Pharmacy Manual for further information regarding the storage conditions of reconstituted ALXN1210.

9.1.4. Study Drug Preparation and Infusion

ALXN1210 must NOT be administered as an IV push or bolus injection. Infusions of study drug should be prepared using aseptic technique. The patient's required dose of ALXN1210 will be further diluted into commercially available saline (0.9% sodium chloride; country-specific pharmacopeia) at the volume specified in Table 5. ALXN1210 admixture will be administered to the patient using an IV tubing administration set via an infusion pump. Use of a 0.2 micron filter is required during infusion.

Table 5: Dosing Reference Chart for ALXN1210 Dose Preparation

Dose Type	Body Weight (kg) ^a	Dose (mg)	ALXN1210 Volume (mL)	Saline Volume (mL)	Total Volume (mL)	Minimum Infusion Duration minutes (hours)	Maximum Infusion Rate (mL/hour)
Loading	≥ 40 to < 60	2400	240	240	480	114 (1.9)	253
	≥ 60 to < 100	2700	270	270	540	102 (1.7)	318
	≥ 100	3000	300	300	600	108 (1.8)	333
Maintenance	≥ 40 to < 60	3000	300	300	600	140 (2.4)	250
	≥ 60 to < 100	3300	330	330	660	120 (2.0)	330
	≥ 100	3600	360	360	720	132 (2.2)	328

Please refer to the Pharmacy Manual for additional dose preparation instructions.

^a Body weight as recorded at the last study visit or more recently.

Doses of study drug must only be prepared and dispensed by qualified study personnel. Study drug is to be dispensed only to enrolled patients who are confirmed eligible for participation in this study. Once study drug is prepared for a patient, it can only be administered to that patient. Vials of study drug are for one-time use only and any drug product remaining in the vial should not be used for another patient. Any drug remaining in the infusion tubing or infusion bag should not be used for another patient.

Further details on preparation and dose administration of ALXN1210, as well as disposal of study drug, can be found in the Pharmacy Manual.

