8.3.2.1. Retreatment of Patients who Discontinue ALXN1210 Treatment

A patient who discontinues ALXN1210 treatment, but remains in the study, and develops abnormal TMA parameter (as indicated by criteria No. 1 below) before Day 1863, may be restarted on ALXN1210, if all 3 conditions below are fulfilled:

1. Evidence of TMA, including thrombocytopenia, evidence of hemolysis, or kidney injury based on any one of the following laboratory findings:
 - Platelet count $< 150,000/\mu\text{L}$, or
 - LDH $> 1.5 \times \text{ULN}$ with hemoglobin $\leq \text{LLN}$ for age and gender, or
 - Serum creatinine $\geq \text{ULN}$ in adults (≥ 18 years of age), or $\geq 97.5^{\text{th}}$ percentile for age ([Appendix A](#)) in adolescents (12 to < 18 years of age).

Note: The TMA laboratory parameter must be confirmed on at least one repeated measure. The above laboratory results can be obtained at either the central laboratory (preferable) or the site's local laboratory.

2. The Investigator believes that the patient will potentially benefit from retreatment, initiates a discussion with the Sponsor Medical Monitor, and provides a medically justified rationale. The Investigator and Medical Monitor mutually agree on retreatment, and the decision is documented.
3. The patient agrees to the consent addendum for retreatment.

If the decision to re-treat with ALXN1210 occurs on a scheduled study visit, then dosing may begin on that day.

- Patient will receive a loading dose of ALXN1210 IV based on the weight recorded at the last visit or more recently (2400 mg for patients weighing ≥ 40 to < 60 kg, 2700 mg for patients weighing ≥ 60 to < 100 kg, 3000 mg for patients weighing ≥ 100 kg). All assessments will be performed per the protocol schedule ([Table 2](#) and [Table 3](#)). If start of the retreatment occurs on a visit which does not include PK/PD sample collection, PK/PD samples will be collected predose and at EOI, along with a predose ADA sample.
- Two weeks after the loading dose, the patient will receive a supplemental maintenance dose of ALXN1210 IV at an unscheduled visit, based on the weight at the last visit or more recently (≥ 40 to < 60 kg = 3000 mg; ≥ 60 to < 100 kg = 3300 mg; ≥ 100 kg = 3600 mg). An abbreviated physical examination will be conducted, vital signs will be collected, and the safety card will be reviewed with the patient. Pharmacokinetic/PD samples will be collected predose and at EOI along with a predose ADA sample.

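### Minor: Protocol Table 5 prints a 140-minute minimum for the 40 to <60 kg maintenance infusion, where the row's own hours and rate both give 144 minutes

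*Protocol*

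**What the plan says.** Table 5 in Protocol section 9.1.4 is the dose preparation chart. Its last two columns are headed "Minimum Infusion Duration minutes (hours) Maximum Infusion Rate (mL/hour"), so each row gives one duration in two units and a rate cap that should correspond to it. For the 40 to <60 kg maintenance dose the row is "3000 300 300 600 140 (2.4) 250": 3000 mg, 300 mL of drug, 300 mL of saline, 600 mL in total, at least 140 minutes (2.4 hours), at most 250 mL/hour.

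The row governs every maintenance infusion in that weight band: Days 15, 71 and 127, then every 8 weeks in the Extension Period. It also governs retreatment under section 8.3.2.1: "Two weeks after the loading dose, the patient will receive a supplemental maintenance dose of ALXN1210 IV at an unscheduled visit". That section gives the dose but no duration or rate of its own. Section 9.2 describes the infusion only as lasting about 2 hours, which does not settle the figure. The SAP does not repeat the table.

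**The concern.** The minutes and the bracketed hours are meant to be the same quantity, and 140 minutes is not 2.4 hours. The rate column offers a third reading of the same limit, and it sides with the hours.

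What is at stake is a clear operating limit for infusing a monoclonal antibody. Protocol Appendix C lists slowing the infusion among the responses to a reaction. A site that sets the pump by volume and the printed minimum time would run faster than the same row permits. Section 9.2 requires actual dose administration times to be recorded, so compliance with the minimum duration could also be judged against the wrong number.

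**Working it through.** **Inputs.** All are from Table 5, section 9.1.4, except the drug concentration of 10 mg/mL, which is from Table 4, section 9.1.1.

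**Is the row otherwise sound?** 3000 mg ÷ 10 mg/mL = 300 mL of drug, and 300 + 300 = 600 mL in total. The dose and volume cells are consistent, so 600 mL can be relied on.

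**The duration, three ways.**

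- From the printed hours: 2.4 × 60 = 144 minutes.
- From volume and maximum rate: 600 ÷ 250 × 60 = 144.0 minutes.
- From the printed minutes: 140 ÷ 60 = 2.33 hours, and 600 ÷ (140/60) = 257.1 mL/hour.

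The printed 140 cannot be reproduced from the row's other figures. The excess over the cap is 257.1 − 250 = 7.1 mL/hour, and 7.1 ÷ 250 = 2.9%. The gap in time is 144 − 140 = 4 minutes.

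**Could rounding explain it?** To one decimal, 2.4 hours covers 2.35 to 2.45 hours, or 141 to 147 minutes, and 140 lies outside. Rounding 2.33 up to 2.4 would rescue the hours but not the rate. If 250 mL/hour is itself rounded to the nearest whole number, it covers 249.5 to 250.5 mL/hour, which is 600 ÷ 250.5 × 60 = 143.7 to 600 ÷ 249.5 × 60 = 144.3 minutes.

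**Do the other rows follow the same rule?** Each row was checked with minutes ÷ 60, volume ÷ maximum rate × 60, and volume ÷ (minutes/60).

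| Row | Volume (mL) | Printed min (h) | Printed max (mL/h) | Minutes ÷ 60 | Minutes from max rate | Rate at printed minutes | Rate minus max |
|---|---|---|---|---|---|---|---|
| Loading, 40 to <60 kg | 480 | 114 (1.9) | 253 | 1.90 | 113.8 | 252.6 | −0.4 |
| Loading, 60 to <100 kg | 540 | 102 (1.7) | 318 | 1.70 | 101.9 | 317.6 | −0.4 |
| Loading, ≥100 kg | 600 | 108 (1.8) | 333 | 1.80 | 108.1 | 333.3 | +0.3 |
| **Maintenance, 40 to <60 kg** | **600** | **140 (2.4)** | **250** | **2.33** | **144.0** | **257.1** | **+7.1** |
| Maintenance, 60 to <100 kg | 660 | 120 (2.0) | 330 | 2.00 | 120.0 | 330.0 | 0.0 |
| Maintenance, ≥100 kg | 720 | 132 (2.2) | 328 | 2.20 | 131.7 | 327.3 | −0.7 |

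In five rows the minutes equal the hours times 60 exactly, and the rate agrees to within 1 mL/hour. Only the 40 to <60 kg maintenance row fails, and it fails both checks. With 144 in place of 140, 144 ÷ 60 = 2.4 hours and 600 ÷ 2.4 = 250.0 mL/hour, so the row closes.

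**The case against.** The best reply is that the row already protects the patient. The minimum duration and maximum rate apply together, and section 9.1.4 requires an infusion pump. A pump held at 250 mL/hour or less takes at least 144 minutes to deliver 600 mL, whichever minimum is printed. Only someone who worked from the minutes alone would go wrong, and then by 4 minutes. This stands, and it is why the point is minor. It does not make the figure right: a chart that staff use to set a pump should not give a minimum time that cannot be used without breaking the limit beside it.

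Two cautions also have some force. The case turns on one character, and no second copy of the table exists in the documents to check it against, so a transcription fault in the public text cannot be wholly excluded. The rest of the row is intact and consistent, which makes that less likely, and the sponsor can settle it from the source table. Section 9.1.4 also refers sites to the Pharmacy Manual, which is not among the documents and may already say 144. Any practical effect at sites is therefore unknown.

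It could be added that the comparison rows are not perfectly rounded: 720 ÷ 2.2 = 327.3 is printed as 328, and 333.3 as 333. That is true, but these differences are below 1 mL/hour, against 7.1 in the faulty row.

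**Conclusion.** The concern holds as a minor error. The minutes figure in the 40 to <60 kg maintenance row should be 144 if the 2.4 hours and 250 mL/hour beside it are as intended. The printed value is 4 minutes short and implies a rate 2.9% above the row's own maximum. An infusion of 144 minutes or longer meets every figure in the row, so the inconsistency bites only between 140 and just under 144 minutes. No endpoint, sample size or planned analysis depends on it. The documents do not say how many patients fall in this weight band, so the number of infusions concerned cannot be given.

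The conclusion rests on two assumptions: that the figure reads 140 in the sponsor's source table, and that the two figures which agree are the intended ones. If the sponsor had instead meant 140 minutes, both the hours and the rate would need correcting.

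**What to change.** In Table 5, change the duration in the 40 to <60 kg maintenance row from 140 (2.4) to 144 (2.4), after the sponsor has compared the row with its source table and confirmed that 250 mL/hour is the intended limit. Check whether the Pharmacy Manual carries the same figure and align it if so. The cost is one number in one table row plus that check. Nothing in the SAP changes.

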9.1.5. Study Drug Handling and Disposal

All clinical study material provided to the Investigator will be stored in a secure place, and allocated and dispensed by appropriately trained persons. Detailed records of the amounts of the investigational product received, dispensed, and destroyed will be maintained.

Unless otherwise notified, empty vials and vials with residual materials should be kept for inspection and accountability by the study monitor prior to their destruction or handled per local pharmacy standard operating procedures (SOPs) for clinical study drugs. To satisfy regulatory requirements regarding drug accountability, at the end of the study all remaining ALXN1210 inventory will be reconciled and destroyed or returned to Alexion according to applicable regulations.

Please refer to the ALXN1210 Pharmacy Manual for further information.

9.2. Treatments Administered

Patients will receive ALXN1210 for 26 weeks during the Initial Evaluation Period. ALXN1210 will be administered as an IV infusion over approximately 2 hours. **ALXN1210 must NOT be administered as an IV push or bolus injection.**

The dose regimen for ALXN1210 during the Initial Evaluation Period is based on the patient's last recorded study visit body weight (Table 6). Patients will receive a loading dose of ALXN1210 IV on Day 1, followed by maintenance dosing of ALXN1210 IV on Day 15 and q8w thereafter.

Table 6: Loading and Maintenance Treatment Regimens

Body Weight ^a	Loading Dose (Day 1)	Maintenance Dose (Days 15, 71, and 127)
≥ 40 to < 60 kg	2400 mg	3000 mg
≥ 60 to < 100 kg	2700 mg	3300 mg
≥ 100 kg	3000 mg	3600 mg

^a Body weight as recorded at the last study visit.

After the Initial Evaluation Period, all patients will roll over into an Extension Period (which will continue until the product is registered or approved [in accordance with country-specific regulations] or for up to 4.5 years, whichever occurs first) during which all patients will receive ALXN1210 q8w.

The actual time of all dose administrations (including any retreatment/supplemental dose for retreatment [Section 8.3.2.1]) will be recorded in the patient's eCRF.

9.3. Method of Assignment to Treatment

This is an open-label study. Patients who satisfy all criteria for enrollment will be assigned to study treatment with ALXN1210 at the Baseline Visit (Day 1). The interactive voice- or web-response system (IxRS) will be used to assign vials containing ALXN1210 to each patient.

9.4. Rationale for Selection of Doses in the Study

The weight-based dosages of ALXN1210 in this study (Table 6) are premised on PK/PD data from early development studies in healthy adult volunteers as well as the available data from patients with PNH in an ongoing Phase 1b dose-finding study (ALXN1210-PNH-103) and an ongoing Phase 2 proof-of-concept study (ALXN1210-PNH-201). The selection of ALXN1210 dose regimen for patients with aHUS is based on targeting immediate, complete and sustained inhibition of terminal complement in patients with PNH, which is expected to correspond to immediate, complete and sustained inhibition of terminal complement in patients with aHUS.

9.5. Special Treatment Considerations

Infusion of other monoclonal antibodies has been associated with infusion reactions, with onset typically during or shortly after completion of the infusion. Please refer to Appendix C for guidance on identifying and managing potential drug infusion reactions.

9.6. Prior and Concomitant Medications and Nonpharmacologic Procedures

Prior medications (including vitamins and herbal preparations)—including those discussed in the exclusion criteria ([Section 8.2](#)) and procedures (any therapeutic intervention, such as surgery/biopsy or physical therapy) the patient takes or undergoes within 28 days prior to the start of Screening until the first dose of ALXN1210—will be recorded on the patient’s eCRF. In addition, history of meningococcal vaccination must be collected for the 3 years prior to first dose of study drug, and for patients < 18 years of age at the time of enrollment, vaccination history for Hib and *Streptococcus pneumoniae* must be collected from birth.

All medication use and procedures undertaken during the study will be recorded in the patient’s source document/medical chart and eCRF. This record will include all prescription drugs, herbal products, vitamins, minerals, over-the-counter medications, and current medications.

Concomitant medications will be recorded from the first infusion of study drug through 56 days after the patient’s last dose of study drug. Any changes in concomitant medications also will be recorded in the patient’s source document/medical chart and eCRF. Any concomitant medication deemed necessary for the patient’s standard of care during the study, or for the treatment of any AE, along with the allowed medications described below may be given at the discretion of the Investigator. However, it is the responsibility of the Investigator to ensure that details regarding all medications are recorded in full in the patient’s source document/medical chart and eCRF.

9.7. Prohibited Medications and Procedures

Patients are prohibited from receiving any of the following medications and procedures at any time after the first dose of study drug for all patients in the study (even those who discontinue ALXN1210 treatment but remain in study) until completion of the study or early termination of the patient from the study:

- Eculizumab or other complement inhibitors
- Use of any other investigational drug or device as part of a clinical trial.
- IVIg (unless for an unrelated medical need e.g. hypogammaglobinemia)
- Rituximab
- PE/PI
- New dialysis within the first 48-hour period following the first dose of ALXN1210 unless there is a compelling medical need as assessed by (1) hypervolemia unresponsive to diuretics, (2) refractory electrolyte imbalance, or (3) new-onset uremic encephalopathy. Exceptions must be approved prior to administration of dialysis on a case-by-case basis by the Sponsor.

The following concomitant medications and procedures are allowed under certain circumstances and with the following restrictions:

- Use of other immunosuppressive therapies (such as steroids, mTORi [eg, sirolimus, everolimus], CNI [eg, cyclosporine or tacrolimus]) during the study are not allowed unless: a) part of an established post-transplant antirejection regime, or b) patient has

confirmed anti-complement factor antibodies requiring immunosuppressive therapy, or c) steroids are being used for a condition other than aHUS (eg, asthma), or d) steroids initiated empirically prior to enrollment and are being tapered as standard of care.

Any patients receiving other complement inhibitors (including eculizumab) or undergoing PE/PI after the first dose of study drug will be withdrawn from the study.

9.8. Vaccination

Due to its mechanism of action, the use of ALXN1210 increases the patient's susceptibility to infection. To reduce the risk of infection, all patients must be vaccinated against *N. meningitidis*.

Patients must be vaccinated against *N. meningitidis* within 3 years prior to, or at the time of, receiving the first dose of ALXN1210. Patients who will be treated with drug less than 2 weeks after receiving a meningococcal vaccine must receive treatment with appropriate prophylactic antibiotics until 2 weeks after vaccination. Vaccines against serotypes A, C, Y, W135, and B, where available, are recommended to prevent common pathogenic meningococcal serotypes. Patients must be vaccinated or revaccinated according to current national vaccination guidelines or local practice for vaccination use with complement inhibitors (eg, eculizumab).

It is recognized that some patients who have not been vaccinated against *N. meningitidis* within 3 years prior to receiving the first dose of ALXN1210 may not be able to receive a vaccination at the time of the first dose. Patients who have not been vaccinated prior to initiating ALXN1210 treatment should receive prophylactic antibiotics prior to and for at least 2 weeks after meningococcal vaccination.

Vaccination may not be sufficient to prevent meningococcal infection. Consideration should be given per official guidance and local practice on the appropriate use of antibacterial agents. All patients should be monitored for early signs of meningococcal infection, evaluated immediately if infection is suspected, and treated with appropriate antibiotics, if necessary.

To increase risk awareness and promote quick disclosure of any potential signs or symptoms of infection experienced by the patients during the course of the study, patients will be provided a safety card to carry with them at all times and for 8 months after last dose of ALXN1210.

Additional discussion and explanation of the potential risks, signs, and symptoms will occur at specific time points as part of the review of the patient safety card and throughout the study as described in the Schedule of Assessments (Table 1, Table 2, and Table 3).

Patients < 18 years of age must also be vaccinated against *Haemophilus influenzae* type b (Hib) and *Streptococcus pneumoniae* according to national and local vaccination schedule guidelines, prior to, or at the time of, receiving the first dose of ALXN1210.

Vaccination status for *N. meningitidis*, Hib, and *S. pneumoniae* will be recorded on the patient's eCRF.

